### Risk/Benefit

There are no known risks to low-level laser therapy.

The potential benefits to the patients are improved course of healing after orthognathic surgery.

Data will be stored on Jacobi shared servers using password-protected spreadsheets, that use codes to de-identify patients' names. The list of patient names that correspond to codes will be saved separately in a password-protected spreadsheet, and only the PI will have access the password.

### Participant Recruitment

The patient pool for this study will be drawn from regular patients scheduled to undergo orthognathic surgery at Jacobi Medical Center. Patients who have been cleared for orthognathic surgery already must be in good health and understand the risks of the surgery. The only additional requirements for inclusion are 1) the planned surgery includes bilateral sagittal split osteotomies; 2) patients must be free from pre-operative inferior alveolar neurosensory deficiencies; 3) the patient cannot have an intra-operative

accidental fracture or rupture of the inferior alveolar nerve. The details of the whole orthognathic surgery will be recorded (including maxillary procedure, genioplasty, and direction of positional change of the mandible) but will not alter eligibility for enrolment in the study.

Since 2013, over 30% of the patients treated for orthognathic surgery at Jacobi Medical Center are between the ages of 15 and 18, which is in line with orthognathic surgery in general. As such, the study aims to include these patients in the potential pool of subjects. Because of the significant portion of patients under the age of 18 in general, and their inclusion will allow for age to be examined as a related factor in how healing proceeds. Their inclusion will also allow for an adequate sample size.

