## Background and Significance

Orthognathic surgery is an essential part of correcting dentofacial deformities. The most common surgery for correcting mandibular deformities is the bilateral sagittal split osteotomy (BSSO). The BSSO was first developed in 1957 by Obwegeser(1), and allowed for anteroposterior correction of the mandible in either a Class II or Class III direction. The BSSO has been modified over time to improve surgical stability and reduce negative post-operative sequelae. Despite the modifications, there are still several potential complications that patients may experience. The most common post-operative complications are pain, swelling and nerve dysfunction.

As with any surgery, pain and swelling are unavoidable, but the extent can be variable. A variety of both pharmaceutical and non-pharmaceutical approaches are generally used to improve pain and swelling, including warm compresses, pressure dressings and analgesics. Physical interventions may reduce swelling, which in turn reduces pain, but are limited in their penetration. Meanwhile medications carry their own potential negative consequences; opioids carry a risk for dependence and neutropenia and non-steroidal anti-inflammatories can cause digestive issues, renal problems.

Nerve dysfunction leading to neurosensory deficits are a relatively common side effect of a BSSO, with literature estimating rates between 9% to 84.6% (2, 3) The inferior alveolar nerve (IAN) runs through the mandibular canal in the body of the mandible, with a branch, the mental nerve, splitting off and exiting the bone at the mental foramen between the first and second premolars. The IAN provides sensation to the gingiva and teeth, while the mental nerve provides sensation to the lips and the chin. During the BSSO, the IAN is necessarily moved and is at risk for either direct or indirect injury, which leads to the neurosensory deficits which are usually transient, but can be permanent in some cases (4-7). Therapy for IAN dysfunction is limited.

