### **Study Design**

The study will have two groups into which patients will be assigned to a control group and an experimental group through a random number generator. Patients will undergo their planned surgical procedure and receive instructions as per standard clinic protocols, in both pre- and post-operative settings. The standard instructions include information on pain and swelling management. The patients will also receive post-operative medications, including an NSAID and an opioid for pain management and a steroid to reduce inflammation and swelling. The patients will be seen at one-week intervals for six weeks for post-operative follow-ups, as per standard clinic protocols. The experimental group will undergo low level laser therapy (LLLT) at weekly intervals. Subject treatment assignments will remain blinded until the final subject has completed follow up and all data has been recorded and validated. Urgent, immediate unblinding due to medical emergency may be authorized by the Investigator. When possible, the treatment assignment will be provided to the treating physician in order to maintain the blind for the Investigator and study staff. All instances of subject unblinding will be documented in the study record.

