To evaluate nerve function, three tests will be conducted, a two-point discrimination (TPD) test, a hard stimulus test and soft stimulus test. For the TPD test, the patient will be instructed to close their eyes, and a caliper will be placed on the lateral aspect of the patient's chin. The calipers will start at 0 mm and be incrementally opened in .5mm increments, and the first distance felt by the patient as two distinct points will be recorded reported in millimeters. For the soft- and hard- stimuli tests, the lower face will be divided into eight regions, with four symmetric regions per side. Region 1 will be from the skin on the chin at the midsagittal plane laterally 1 cm. Region 2 will be the skin from the edge of Region 1 extending laterally 1 cm. Region 3 will be the skin from the edge of Region 2 extending laterally 1 cm. Region 4 will be the vermillion of the lower from the midsagittal plane to the commissure. The regions will be designated by an "L" for left or "R" for right, plus a number as per the above scheme. Each region will be checked for nerve function via two tests, a cotton-swab test and a two test. During the evaluation, the patient will be instructed to keep their eyes closed. The cotton-swab test will involve the skin in each region being lightly brushed in a 2cm vertical path twice per region, and the patient reporting if they feel the contact. Likewise, the toothpick test will involve the skin being slightly depressed by the edge of a toothpick in three spots separated by 1 cm each per region, and the patient reporting if they feel the contact. The responses will be recorded as positive or negative for soft (swab) or hard pressure (toothpick), by region.

Pain will be reported via use of a visual analogue scale (VAS). The patient will rate the intensity of the pain on each side of the mandible at each visit. The intensity of the pain will be from zero, meaning complete absence of pain, to 10, indicating the maximum amount of pain imaginable.

Swelling will be measured with a soft measuring tape from the tip of the chin to the lower lobe of the ear, bilaterally. The calculation of the swelling index will be done by subtracting the baseline length (from the six-week post-operative visit) to the measured length and dividing the difference by baseline length and multiplying by 100.

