### **Data analysis**

The primary outcome, change in neurosensory deficit, is measured by the three clinical tests, TPD, soft-stimulus and hard-stimulus. For TPD, the difference between the LLLT group and placebo group at each time point will be compared using an independent t-test, with alpha set at .05. The soft- and hard-stimulus tests for each region will be analyzed at each time point with a chi-square test. VAS pain score and swelling index will be analyzed using independent t-tests for the measurements on each side at each time point, with alpha set at .05. Linear regression will be performed to analyze the relationship of the pain, swelling and nerve tests with age, skeletal class, direction and magnitude of mandibular movement, and inclusion of genioplasty.

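### The laser comparison of TPD, read only on the chin, is not adjusted for genioplasty, although genioplasty is allowed, recorded and named by the plan as a possible predictor

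*Combined protocol and SAP*

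**What the plan says.** - **Eligibility (Participant Recruitment).** Any patient whose surgery includes the bilateral split osteotomy may enter if the nerve is intact before and during surgery. Other surgical details are recorded, "including maxillary procedure, genioplasty, and direction of positional change of the mandible) but will not alter eligibility for enrolment in the study".
- **Where sensation is measured (Study Design).** For TPD, "a caliper will be placed on the lateral aspect of the patient's chin". For the soft and hard tests, "the lower face will be divided into eight regions, with four symmetric regions per side". Region 1 is named as chin ("Region 1 will be from the skin on the chin at the midsagittal plane laterally 1 cm"); Regions 2 and 3 are the next two 1 cm strips of skin; Region 4 is the lower-lip vermilion.
- **Nerve supply (Background and Significance).** The inferior alveolar nerve serves gingiva and teeth, "while the mental nerve provides sensation to the lips and the chin".
- **Allocation (Study Design).** Patients are "assigned to a control group and an experimental group through a random number generator". No stratification or blocking is stated.
- **Analysis (Data analysis).** For TPD, "the difference between the LLLT group and placebo group at each time point will be compared using an independent t-test". The soft and hard tests get a chi-square test for each region and visit. A separate linear regression relates pain, swelling and nerve tests to age, skeletal class, mandibular movement and genioplasty. Treatment group is not among its listed terms.

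**The concern.** Genioplasty is a further procedure on the chin, where TPD is read. If it affects chin sensation, as the plan allows for by listing it as a regressor, two things follow. Its contribution sits in the error term of the t-test and reduces power. And if one arm happens to receive more genioplasty patients, the observed TPD difference moves by an amount unrelated to the laser.

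Nothing else in the plan removes this. The nerve baseline is pre-operative, so a genioplasty effect arises after it and stays in any change score. The eligibility rules screen for inferior alveolar deficits before surgery and damage to that nerve during it, not for a chin procedure.

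**Working it through.** **Inputs from the documents:** difference 0.5, SD 0.5, power 90%, 23 per arm, 46 in all (Sample Size); alpha 0.05 (Data analysis). The units of the 0.5 are not stated; it is read here as being on the TPD scale. Two-sided testing is assumed.

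**Inputs assumed, because the documents give none:** genioplasty share p = 20% to 50%; genioplasty effect on TPD g = 0.25, 0.5 or 1.0.

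**1. The plan's sample size.** Normal approximation: n per arm = 2 × (1.960 + 1.282)² × (0.5/0.5)² = 21.01. The exact t-test calculation gives 22.02, hence 23, which matches the plan. Power at 23 per arm is 0.912.

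**2. Chance of an imbalance of 20 points or more.**
- Simple randomisation of 46 (simulation): about 10%, 15% and 19% for p = 20%, 30% and 50%.
- Arms fixed at 23 and genioplasty counts fixed at 9, 14 and 23 (hypergeometric): 13%, 11% and 24%. The order is uneven because counts are whole numbers.

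**3. Size of the shift.** Shift = imbalance × g. At 20 points: 0.2 × 0.25 = 0.05; 0.2 × 0.5 = 0.10; 0.2 × 1.0 = 0.20. Divided by 0.5, these are 10%, 20% and 40% of the planned difference.

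**4. Operating characteristics with residual SD 0.5.** Simulation, 23 per arm, p = 20%, 30% and 50%; ranges are over p.

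| g | Unadjusted type I error, all trials | Unadjusted type I error, trials with gap ≥ 20 points | Unadjusted power, all trials | Unadjusted power, gap ≥ 20 points against the laser |
|---|---|---|---|---|
| 0.25 | 0.05 | 0.06–0.07 | 0.89–0.90 | 0.80–0.82 |
| 0.5 | 0.05 | 0.09–0.12 | 0.84–0.87 | 0.59–0.66 |
| 1.0 | 0.05 | 0.16–0.24 | 0.64–0.73 | 0.12–0.24 |

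With treatment and genioplasty in the model, type I error is about 0.05 in every setting, including the imbalanced trials. Power is 0.90–0.91 overall and 0.88–0.90 under adverse imbalance.

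**5. The same question with the planned 0.5 taken as the total SD.** A yes/no factor contributes variance p(1−p)g², so the residual variance is 0.25 − p(1−p)g². Example, p = 30% and g = 0.5: 0.25 − 0.21 × 0.25 = 0.1975, residual SD 0.444, power about 0.96 with 43 degrees of freedom. Over p = 20% to 50%, power rises from 0.91 unadjusted to about 0.92–0.93 (g = 0.25) or 0.95–0.97 (g = 0.5).

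**6. How large g can be.** Under a total SD of 0.5, g cannot exceed 0.5/√(p(1−p)): 1.25, 1.09 and 1.00 for p = 20%, 30% and 50%. So g = 1.0 is at or near the limit, and the g = 1.0 row in step 4 implies a total SD above the planned one: √(0.25 + 0.21) = 0.68 at p = 30%.

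**The case against.** The strongest reply is that randomisation already deals with chance imbalance. The unadjusted t-test is unbiased over repeated trials and keeps its 5% error rate. This is correct, and step 4 confirms it. A reader might infer that allowing genioplasty inflates the trial's false-positive rate; the documents do not support that. The raised rates in the table apply only within the minority of trials that turn out imbalanced.

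The second reply is that the size is unknown. This also stands. Listing genioplasty as a regressor shows interest, not an established effect, and the Background attributes nerve deficits to the split osteotomy. A reader might suppose a genioplasty effect of 2 mm, so that a 20-point gap would give 0.4, or 80% of the planned difference. That cannot fit the planned SD (step 6). If the true SD is nearer the 1.56 to 1.62 reported for one cited study, even a 0.20 shift is only about 0.125 SD (0.20/1.6).

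Third, a reader might infer that six of the eight stimulus regions lie on the chin and only the lip is spared. Only Region 1 is called chin, and the plan gives lip and chin the same nerve, so that split does not mark who is affected.

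Fourth, the plan does not ignore genioplasty: it is recorded and regressed on. That narrows the gap but does not close it, because a regression without treatment gives no laser effect. Enrolling all split-osteotomy patients is a defensible choice and is not criticised here.

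**Conclusion.** The point holds as a gap in the analysis, not as a flaw in eligibility or a threat to the overall error rate. The plan collects a factor that it regards as a possible predictor of its primary outcome, then leaves it out of the comparison that tests the laser.

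The size depends on the assumed share and effect. At g = 0.25 the loss is small. At g = 0.5, unadjusted power averages 0.84–0.87 if 0.5 is the residual SD; if 0.5 is the total SD, adjustment lifts power from 0.91 to 0.95–0.97. The 40% shift needs both a 20-point gap and g = 1.0, so it is an upper case. A reader should not conclude that imbalance is likely to produce a shift as large as the effect sought.

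The change is worth making because it costs almost nothing even if genioplasty has no effect. The genioplasty is done at surgery and the laser starts on post-operative day 1, so treatment cannot influence the factor and adjusting for it is legitimate.

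**What to change.** - **Data analysis, TPD:** before unblinding, pre-specify a linear model with treatment and genioplasty (yes/no) as the primary laser comparison, in place of the bare t-test. The unadjusted result can be shown beside it.
- **Data analysis, soft and hard tests:** report a genioplasty-adjusted treatment effect as a supporting analysis, for example from a logistic model that allows for several regions per patient. Do not split every region-by-visit table: at a 20% share there would be about 9 genioplasty patients, 4 or 5 per arm, and the tables would be too sparse.
- **Study Design, allocation:** if allocation has not started, stratifying the random list by planned genioplasty is optional. It requires that the surgical plan be settled at randomisation, which the documents do not state. If the list is in use, the analysis change is enough.

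Cost: one degree of freedom (43 instead of 44 at 46 patients), a few sentences in the plan, and no added patients, visits or data.

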### **Informed Consent**

Patients who express interest in volunteering for the study will have the risks and benefits of the study explained to them, as well as that they may be assigned to either a control or experimental group. The details of study participation will be explained, including that the patients will not have any aspect of their surgery or post-care altered, other than LLLT treatment. It will be explained that the time commitment of the study is the same as the normal post-op care, with the exception of two additional visits at 8 weeks and 20 weeks post-op. It will be explained that patients may decide to not volunteer and their treatment will not be affected. Likewise, if the patients decide to drop out of the study, their treatment will not be affected. Information security will also be discussed with the patient during the consent process. All information in the discussion will be provided to the patient in written form, with a copy for them to keep. Patients who desire an alternate language will be offered translation services.

Patients over 18, will be given an informed consent form to sign. Patients who are under 18 will be asked to sign the informed consent form, to indicate their assent, while a legal guardian, who will also be present for the discussion of the risks and benefits of the study, will be asked to sign for consent.

### **Data analysis**

The primary outcome, change in neurosensory deficit, is measured by the three clinical tests, TPD, soft-stimulus and hard-stimulus. For TPD, the difference between the LLLT group and placebo group at each time point will be compared using an independent t-test, with alpha set at .05. The soft- and hard-stimulus tests for each region will be analyzed at each time point with a chi-square test. VAS pain score and swelling index will be analyzed using independent t-tests for the measurements on each side at each time point, with alpha set at .05. Linear regression will be performed to analyze the relationship of the pain, swelling and nerve tests with age, skeletal class, direction and magnitude of mandibular movement, and inclusion of genioplasty.

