### **Sample Size**

Published data (13-15) examining the effect of LLLT on IAN functional recovery shows a range of improvement versus placebo. The percentage of recovery shows that the LLLT treatment led to 27.3% (n=30, not split mouth, standard deviation not reported) (13), 13% (n=12, split mouth,  $7.4167 \pm 1.62$  vs  $8.5000 \pm 1.56$ ) (14), and 15% (n= 15,  $5.12 \pm 0.59$  vs  $5.97 \pm 0.45$ ) (15) improvement in sensory function, with . Additionally, one non-placebo controlled study of patients with long-standing documented neurosensory alteration following dental surgery (12) showed 33% improvement over baseline (n=4).

Using these studies, a sample size graph (Figure 1) was plotted in R Stats Package with the effect size versus sample size, with the standard deviation set to 0.5 and power set to 0.9. In order to detect an effect size of 0.5 with a SD of 0.5 at 90% power a sample size of just over 22 is needed. Therefore, 23 subjects per arm is required.

[figure not shown]

Figure 1- Effect size vs. Sample size.

The oral surgery clinic at Jacobi Medical Center treats approximately 50 patients with orthognathic surgery of the mandible annually, and has done so routinely for the last decade. Recruiting 46 patients to participate, even accounting for potential drop outs or failure to follow-up, should prove feasible.

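### Age is modelled apart from treatment arm; one prespecified model containing both would guard precision and correct chance age imbalance at almost no cost

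*Combined protocol and SAP*

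**What the plan says.** The Participant Recruitment section reports that over 30% of the clinic's orthognathic patients "are between the ages of 15 and 18". It includes them for sample size and because "their inclusion will allow for age to be examined as a related factor in how healing proceeds". It gives no upper age limit.

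The Study Design section assigns patients by a random number generator and mentions no stratification by age.

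In the Data analysis section every between-arm comparison is unadjusted:
- For TPD, "For TPD, the difference between the LLLT group and placebo group at each time point will be compared using an independent t-test".
- The soft- and hard-stimulus tests are compared by chi-square, by region and visit.
- Pain (VAS) and swelling index are compared by t-tests, by side and visit.

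Age appears in one further sentence: "Linear regression will be performed to analyze the relationship of the pain, swelling and nerve tests with age". That sentence goes on to list skeletal class, direction and magnitude of mandibular movement, and genioplasty. Treatment arm is not among the terms, and the regression is not presented as a treatment comparison.

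**The concern.** The plan picks out age as a variable worth relating to the outcomes, but models it away from the analysis that answers the trial's main question. As written, the age regression does not estimate a laser effect, and the laser tests take no account of age.

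If age is related to nerve recovery, two things follow. Age variation stays in the error term of the TPD comparison and costs precision. And if one arm happens to receive more teenagers, part of the observed arm difference reflects age and nothing in the plan removes it. With 46 patients, noticeable imbalances are not rare. Age is known before surgery and is already to be analysed, so the remedy needs no new data.

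**Working it through.** **Inputs from the documents.** Alpha 0.05 (Data analysis; two-sided assumed). Difference 0.5, SD 0.5, power 0.9 and 23 per arm (Sample Size: "detect an effect size of 0.5 with a SD of 0.5 at 90% power" and "Therefore, 23 subjects per arm is required"). Share aged 15-18: over 30%, taken as 30% (Participant Recruitment).

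**Input assumed.** The share of TPD variance explained by age, R². The documents give no figure. The range used is 0 to 0.30, with 0.10-0.30 as the case where age matters. The planned SD of 0.5 is taken to include age variation unless stated otherwise.

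**1. The plan's own figure.** A two-sample t-test with standardised difference 0.5/0.5 = 1.0, two-sided alpha 0.05 and 90% power needs 22.02 per arm, hence 23. This matches the plan. Power at 23 per arm is 91.2%.

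**2. Chance of imbalance.** Take the number aged 15-18 in each arm as Binomial(23, 0.30), independently.
- P(difference of at least 4; 4/23 = 17 percentage points) = 0.259
- P(at least 5; 22 points) = 0.146
- P(at least 6; 26 points) = 0.075

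**3. Shift caused by a 5-patient imbalance.** If the age effect is a gap g in mean TPD between teenagers and adults, it contributes variance 0.30 × 0.70 × g² = 0.21 g². Setting this equal to R² × 0.5² gives g = √(0.25 R² / 0.21). The shift in the arm difference is (5/23) × g.

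| R² | g (mm) | Shift (mm) | Share of planned 0.5 |
|---|---|---|---|
| 0.10 | 0.35 | 0.075 | 15% |
| 0.20 | 0.49 | 0.106 | 21% |
| 0.30 | 0.60 | 0.130 | 26% |

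**4. Precision and power with age in the model.** The standard error is multiplied by √[(1 − R²)(1 + 1/42)]. The factor 1 + 1/42 allows for expected chance imbalance in age, with 2 × 23 − 4 = 42. Residual df fall from 44 to 43.

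| R² | SE factor | Power at difference 0.5, SD 0.5 |
|---|---|---|
| unadjusted | 1 | 91.2% |
| 0 | 1.01 | 90.6% |
| 0.10 | 0.96 | 93.2% |
| 0.20 | 0.91 | 95.6% |
| 0.30 | 0.85 | 97.5% |

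**5. If 0.5 is instead the SD among patients of the same age.** The total SD is then 0.5/√(1 − r²), where r is the age-TPD correlation. Unadjusted power is 90.1% at r = 0.2, 88.6% at r = 0.3 and 81.9% at r = 0.5. Adjustment keeps about 90.6% throughout.

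**6. Validity of the unadjusted test.** In 100,000 simulated trials at each of r = 0.3 and r = 0.5, overall type I error was 5.0%. In the roughly 9% of trials where mean age differed between arms by at least 0.5 SD of age, it was 8.9% (r = 0.3) or 15.3% (r = 0.5). Where the gap was below 0.2 SD it was 4.1% or 2.7%. The average holds because these cases offset one another.

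**The case against.** The strongest reply is that nothing is broken. Randomisation makes the unadjusted comparison unbiased, and its standard error already allows for chance imbalance. At the plan's design point power is above target without adjustment. The size of any gain rests on an age effect that the documents do not quantify. If the SD of 0.5 includes age variation and r is 0.2, adjusted power is 91.7% against 91.2%, a gain of half a point. All of this stands, and it limits the point to efficiency and to protection in the trial actually run.

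Four stronger readings are tempting, and the documents do not support them.
- A reader might infer that the plan expects age to affect healing. It proposes only to examine the question.
- A reader might infer that leaving age out biases or invalidates the primary result. Step 6 shows that it does not; the raised error rates are conditional on a large age gap.
- A reader might infer that allocation is simple and therefore unbalanced on age by design. The Study Design section does not say whether it is simple or stratified. Step 2 describes what happens if it is not stratified by age.
- A reader might assume a 1.0 mm teenager-adult gap, making the 5-patient shift 5/23 = 0.22 mm, or 43% of the planned difference. At an SD of 0.5 that gap would need age to explain 0.21 × 1.0²/0.25 = 84% of TPD variance, which is not credible beside an assumed 10-30%.

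It can also be said that age is only one of several covariates in the planned regression. That is fair. Age is singled out here because the plan gives it as a reason for enrolling minors, and because it is a simple baseline measure available for every patient.

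**Conclusion.** The point holds as a low-cost improvement and not as a flaw in validity. No laser-versus-placebo comparison includes age, no age stratification is stated, and the age regression names no arm.

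The gain and the cost are unequal. If age explains 10-30% of TPD variance, prespecified adjustment lifts power from 91.2% to between 93.2% and 97.5%. It also corrects for an imbalance that, at 5 patients, would move the estimate by 0.08-0.13 mm (15-26% of the planned difference); an imbalance of that size or larger has a 15% chance. If age explains nothing, power goes from 91.2% to 90.6%.

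These figures rest on the assumed R², a 30% share aged 15-18, allocation not stratified by age, all 46 patients analysed and, for the shift, an age effect that acts as a step between the two age groups. Prespecification matters because adding age after an imbalance has been seen would be open to challenge.

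**What to change.** In the Data analysis section:
- Make the primary between-arm comparison of TPD at each visit a linear model with treatment arm and age in years as terms. Report the arm coefficient with its 95% confidence interval. Do the same for VAS and swelling index.
- For the soft- and hard-stimulus tests, use a logistic model with the same two terms, so that age is handled in the same way for every outcome.
- Keep the planned t-tests and chi-square tests as supportive analyses, and say that the adjusted models are primary.
- Read the age question from these same models, so that the age association is also adjusted for arm.
- State whether allocation is stratified by age.

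The cost is a few sentences and one degree of freedom per linear model, with the small loss of power given above if age proves unrelated to outcome. No extra data, visits or patients are needed.

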The proposed LLLT protocol will use the Biolase Epic X, an InGaAsP diode laser (940nm) using the pain relief handpiece, a device which has received FDA approval (GUDID 00647529002537) for the treatment of pain, muscle relaxation and healing via increased local circulation. The LLLT will be administered to the experimental group at 30 j/cm^2. The laser will be applied extraorally, on the skin overlying the mandible. Application will be for 40 seconds per side, with 10 seconds administered in four places along the jawline, 1 cm apart starting from the gonial angle. The timing would coincide with standard post-operative care, with the first LLLT administration performed on post-operative day 1, prior to the patient's discharge from the hospital. The follow-up LLLT doses would be given at the standard post-op follow-up visits, at one-week intervals, which would be at week 1, week 2, week 3, week 4, week 5, and week 6. Patients will be seen for evaluation at week 8 and again at approximately 20 weeks post-surgery. The control group will follow the same post-op visit schedule, but receive a dummy treatment in which the laser handpiece is moved over the patient's jaw in a similar fashion as the experimental but without laser irradiation.

Nerve function, pain and swelling will be measured according to objective measures. A baseline measurement will be recorded pre-operatively for nerve function and pain. Baseline for swelling will be used from the final measurement at week 8, due to the changes in mandible length caused by the orthognathic surgery. Measurements for each outcome will also be performed on the days for which

LLLT is administered. The individual who performs the assessment will be blinded to the group to which each patient belongs.

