### **Outcomes (primary and secondary)**

In this study, the predictor variable was the use of laser therapy versus placebo treatment after orthognathic surgery on the mandible. The primary outcome variable was neurosensory disturbance recovery by the TPD, hard and soft sensory tests. The secondary outcome variables are pain reduction, as measured by change in VAS, and swelling reduction, as measured by soft-ruler measurement of lower face.

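### The pre-operative TPD and VAS are collected but not used in the arm comparison; the TPD test variable is not named, and the VAS test does not match its definition as change

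*Combined protocol and SAP*

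**What the plan says.** The Data analysis section describes the primary outcome as a change: "The primary outcome, change in neurosensory deficit, is measured by the three clinical tests". The Outcomes section words it as recovery, "The primary outcome variable was neurosensory disturbance recovery by the TPD, hard and soft sensory tests", and defines pain as a change: "The secondary outcome variables are pain reduction, as measured by change in VAS". Study Design provides the baseline for both: "A baseline measurement will be recorded pre-operatively for nerve function and pain".

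The planned arm comparisons in Data analysis are:

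- TPD: "the difference between the LLLT group and placebo group at each time point will be compared using an independent t-test", at alpha 0.05.
- Pain and swelling: "VAS pain score and swelling index will be analyzed using independent t-tests for the measurements on each side at each time point".

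The same section plans a linear regression on age, skeletal class, mandibular movement and genioplasty. It lists neither treatment arm nor the baseline value, so the plan states no baseline-adjusted laser effect.

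The Sample Size section sets 23 per arm to "detect an effect size of 0.5 with a SD of 0.5 at 90% power". It does not say whether that SD belongs to a visit value or to a change.

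**The concern.** The two measures have different problems.

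For TPD, the variable entering the t-test is not named. A test of visit values and a test of changes from the pre-operative measurement both fit the sentence. They can give different p-values and have different power, so the choice could be made after the data are seen.

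For VAS, the variable is identifiable. The section tests the pain score as measured on each side at each visit, which means values. That does not match the Outcomes section.

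For both, a baseline that is already being collected plays no part in estimating the laser effect. At stake are some precision and a clear match between outcome and analysis. The swelling index (already relative to a baseline) and the stimulus tests (chi-square) are outside this point, and the regression on patient and surgical factors is not criticised.

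**Working it through.** **Inputs from the documents.** Difference 0.5, SD 0.5, so d = 0.5/0.5 = 1.0; power 90%; 23 per arm, N = 46 (Sample Size). Alpha 0.05 (Data analysis); sidedness is not stated, but two-sided reproduces the plan's figure. The split-mouth study cited in Sample Size, treated here as two independent groups, gives d = (8.5000 - 7.4167)/sqrt((1.62² + 1.56²)/2) = 0.68.

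**Assumptions, since the documents give no figure.** Correlation r between the pre-operative and post-operative value: 0, 0.3, 0.5, 0.7. Ratio s of pre-operative to post-operative SD: 1, 0.5, 0.25. The SD of 0.5 is taken to be that of a single post-operative value.

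**Step 1: the plan's own figure.** A two-sided t-test at d = 1.0 with 90% power needs 22.02 per arm, rounded up to 23. (One-sided gives 18.) At 23 per arm the noncentrality is 1.0 × sqrt(23/2) = 3.39 on 44 df, and power is 0.912. The stated sample size reproduces.

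**Step 2: the three analyses at one time point.**

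- Values: noncentrality d × sqrt(23/2), 44 df.
- Change scores: divide that by sqrt(1 + s² - 2rs), 44 df. Example: r = 0, s = 1 gives 3.39/sqrt(2) = 2.40, power 0.650.
- ANCOVA with one covariate: divide by sqrt((1 - r²)(1 + 1/42)), 43 df, where 42 = 46 - 1 - 3. Example: r = 0.5 gives 3.39/0.876 = 3.87, power 0.966.

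| d | Analysis | r = 0 | r = 0.3 | r = 0.5 | r = 0.7 |
|---|---|---|---|---|---|
| 1.0 | Values | 0.912 | 0.912 | 0.912 | 0.912 |
| 1.0 | ANCOVA | 0.906 | 0.930 | 0.966 | 0.996 |
| 1.0 | Change, s = 1 | 0.650 | 0.800 | 0.912 | 0.990 |
| 1.0 | Change, s = 0.5 | 0.843 | 0.925 | 0.969 | 0.994 |
| 1.0 | Change, s = 0.25 | 0.896 | 0.935 | 0.957 | 0.975 |
| 0.68 | Values | 0.618 | 0.618 | 0.618 | 0.618 |
| 0.68 | ANCOVA | 0.607 | 0.648 | 0.731 | 0.878 |
| 0.68 | Change, s = 1 | 0.359 | 0.480 | 0.618 | 0.831 |
| 0.68 | Change, s = 0.5 | 0.524 | 0.640 | 0.742 | 0.861 |
| 0.68 | Change, s = 0.25 | 0.592 | 0.657 | 0.708 | 0.763 |

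The other cited study with SDs gives d = (5.97 - 5.12)/sqrt((0.59² + 0.45²)/2) = 1.62. There the plain t-test already exceeds 99%.

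**Step 3: the likely range for TPD.** Participant Recruitment excludes pre-operative inferior alveolar deficits, so pre-operative TPD probably varies little and r is probably low. For r from 0 to 0.3, ANCOVA minus values is -0.7 to +1.7 points at d = 1.0, and -1.1 to +3.0 points at d = 0.68. ANCOVA overtakes values at r of about 0.16.

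**Step 4: robustness.** Over the 24 combinations (2 d × 4 r × 3 s), ANCOVA is never more than 1.1 points below the best of the three methods.

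**Step 5: why the ambiguity goes.** Write the model as Y = a + τ·arm + β·B + error, where B is the baseline. Subtracting B from both sides gives Y - B = a + τ·arm + (β - 1)·B + error. The arm effect τ and its standard error are the same for value and change.

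**The case against.** The strongest case against has four parts.

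1. **TPD most naturally means values.** Study Design says the TPD threshold is recorded in millimetres. Where a baseline-relative variable is wanted, as for swelling, a formula is given; none is given for TPD. With pre-operative deficits excluded, any later deficit is already a change from none. This makes values the likelier reading, but it does not make it a stated one, because the section itself calls the outcome a change.

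2. **The gain is negligible.** For TPD this largely stands: -1 to +3 points in the likely range. A reader of the table might infer that the plan risks losing 26 points of power. The documents do not support that. A shortfall of that size for values appears only at d = 0.68 with r = 0.7. For change scores it appears only at d = 1.0 with r = 0, equal SDs and a change-score test actually being run. These are the extremes of assumed ranges.

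3. **Nothing is quantified for pain.** This stands. Sample Size does not name the measure behind its means, and none of its effect sizes is for VAS.

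4. **ANCOVA is a preference; one sentence saying that visit values are compared would do.** That sentence would remove the ambiguity but leave the collected baseline unused. ANCOVA removes it too, at a worst-case cost of about 1 point in the range examined.

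**Conclusion.** The point holds as a cheap, minor improvement. The TPD test variable is unnamed, the VAS test of values does not match an outcome defined as change, and no baseline-adjusted laser effect is planned although the baseline is collected.

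Two stronger inferences should be resisted. The t-tests are not biased, because randomisation protects them, and the sample size is not wrong for them. Nor is the VAS variable unspecified: it is specified as values, and the fault is the mismatch.

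The size rests on assumed r and SD ratio. For TPD, expect about -1 to +3 points of power over values at r of 0.3 or less, and more only if r is higher (97% against 91% at d = 1.0 and r = 0.5). The change-score route, which the outcome wording invites, would fall to 65% at d = 1.0 if r = 0 and the SDs are equal.

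**What to change.** In Data analysis, for TPD and VAS:

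- Replace the t-test at each post-operative time point with an ANCOVA of the post-operative value on arm, with the pre-operative value of the same measure as covariate. For VAS use the same side. For TPD use the same side, or the same combination of sides, as the outcome.
- Report the adjusted arm difference with its 95% confidence interval.
- State that change-score t-tests will not be used.
- Align the change wording in Outcomes and Data analysis with this model.

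Name this one model and no alternative, so that the choice does not reopen. The existing regression can stay as it is.

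Cost: analysis wording only, with no added visits, staff, patients or measurements. The statistical cost is about 1 point of power if the baseline proves uninformative.
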